## 4.3. Missing Data

Partial dates are allowed on the eCRF for prior anti-cancer systemic therapy start and stop dates, subsequent anti-cancer therapy start date, adverse event (AE) onset and resolution dates, concomitant medication start and stop dates, and concomitant procedure dates. An entry for the year is required in the eCRF system for each of these dates. Only the month and day may be entered as unknown. Dates from these forms will be reported in listings as collected. Every effort will be made to query missing dates.

#### 4.3.1. Missing AE Onset Date

For records with missing AE onset date, the following procedure will be employed for use in determining whether the AE is treatment emergent:

- AE onset dates with missing day and non-missing month will be assumed to occur on the first day of the non-missing month, except for AEs occurring in the first month of dosing, in which case the date will be the first day of dosing.
- AE onset dates with missing month will be assumed to occur on the first day of the non-missing year (ie, January 1), except for AEs occurring in the first year of dosing, in which case the date will be the first day of dosing.

#### 4.3.2. Missing Medication Date

For records with a missing medication (including prior systemic therapy) start and/or stop date, the following procedure will be employed for use in determining whether the medication is prior or concomitant:

Medication start dates with a missing day and non-missing month will be assumed to
occur on the first day of the non-missing month, except for medications occurring in
the first month of dosing, in which case the date will be the first day of dosing.

- Medication start dates with missing month will be assumed to occur on the first day of the non-missing year (ie, January 1), except for medications occurring in the first year of dosing, in which case the date will be the first day of dosing.
- Medications that are not ongoing and have a medication stop date with a missing day and non-missing month will be assumed to occur on the last day of the non-missing month.
- Medications that are not ongoing and have a medication stop date with a missing month will be assumed to occur on the last day of the non-missing year (ie, December 31).

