# **4.3.3.** Missing Procedure Date

For records with a missing procedure (including prior radiotherapy) date, the following procedure will be employed for use in determining whether the procedure is prior or concomitant:

- Procedure dates with a missing day and non-missing month will be assumed to occur on the first day of the non-missing month, except for procedures occurring in the first month of dosing, in which case the date will be the first day of dosing.
- Procedure dates with missing month will be assumed to occur on the first day of the non-missing year (ie, January 1), except for procedures occurring in the first year of dosing, in which case the date will be the first day of dosing.

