#### 4.3.4. Missing Death Date

For records with a partial death date, the following procedure will be employed for use in deriving time-to-event variables (eg, PFS).

• The death date will be imputed by the earliest possible date that is not contradicting with any other available data in the database.

All other data will be reported as they are collected. No imputation methods will be used to replace missing data unless otherwise stated in this document.

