#### 7.7. Concomitant Procedures

All procedures within 14 days before the Cycle 1 Day 1 through 30 days after last study treatment must be recorded on the appropriate eCRF. Prior procedures are defined as occurring before the first dose of study drug (by procedure date). Concomitant procedures are defined as procedures with a procedure date on or after the first dose of study drug, and within 30 days of the last dose of study drug or prior to the start of a new anti-cancer treatment, whichever occurs first.

Prior and concomitant procedures will be coded using MedDRA, associating lower-level terms with PT and SOC by the primary hierarchy. Summary tables will be provided for prior and concomitant procedures. The tables will display number and percentage of patients who reported at least 1 procedure in each SOC represented in the eCRF data. Within each SOC, the tables will display number and percentage of patients reporting at least 1 concomitant procedure as designated by PT.

A complete listing of procedures will be generated. The listing will indicate which procedures are prior and which are concomitant. The listing will display entries from the concomitant procedures form, ordered within patient by date of procedure. The listing will display the recorded term from the eCRF and the SOC and PT.

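### The SAP's partial-date rules can turn known prior systemic therapy and radiotherapy into concomitant treatment, and no rule covers a partial subsequent-therapy start date.

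*SAP*

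**What the plan says.** **Scope and purpose.** SAP 4.3.2 covers prior anticancer drugs by name: "For records with a missing medication (including prior systemic therapy) start and/or stop date". The imputed date is "for use in determining whether the medication is prior or concomitant". SAP 4.3.3 does the same for procedures: "For records with a missing procedure (including prior radiotherapy) date".

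**Start and procedure dates.** If the day is missing, the first of the month is used; if the month is missing, 1 January. There is an exception when the known month or year is that of first dose. For medications it reads "except for medications occurring in the first year of dosing, in which case the date will be the first day of dosing", and for procedures "except for procedures occurring in the first year of dosing, in which case the date will be the first day of dosing". A missing day in the dosing month is treated the same way.

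**Stop dates.** The rule for drugs already stopped is that those which "have a medication stop date with a missing month will be assumed to occur on the last day of the non-missing year"; with only the day missing, the month's final day is used.

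**Classification.** SAP 7.6 calls a medication prior if its stop date precedes first dose. SAP 7.7 uses the single procedure date: "Concomitant procedures are defined as procedures with a procedure date on or after the first dose of study drug".

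**Subsequent therapy.** SAP 4.3 allows a partial start date for subsequent anti-cancer therapy; only the year is mandatory. Sections 4.3.1 to 4.3.4 give rules for AE onset, medications, procedures and death, but none for this date. Section 4.3.4 closes with "No imputation methods will be used to replace missing data unless otherwise stated in this document". The date is used in PFS censoring (6.1.1), in DoR by reference (6.1.4), and in the safety and TEAE windows (7 and 7.2).

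**The concern.** Moving an ambiguous date into the treatment period is a sensible convention for adverse events and ordinary medications, where the timing is truly unknown. It has no rationale for a record from a prior-therapy form, whose source already settles its status.

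The situation can arise under the eligibility rules. Exclusion criterion 3 in protocol 5.2 requires a systemic-therapy washout of 5 half-lives or 4 weeks, whichever is shorter, and 2 weeks for palliative limited-field radiotherapy. Prior treatment in the year of first dose, and sometimes in the same month, is therefore compatible with enrolment. If it is reclassified, the summary tables would show anticancer treatment given alongside study drug, which protocol 8.1.1 generally does not allow.

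For subsequent therapy the problem is a missing rule. The programmer has either no usable date or an unplanned choice, and that choice moves a PFS censoring date and the end of the TEAE window.

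**Working it through.** The plan gives no figure to reproduce. The check applies the written rules to assumed dates.

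**1. Prior therapy, first dose 20 September 2022 (assumed)**

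| Record as collected | Imputed | Result |
|---|---|---|
| Radiotherapy, September 2022, day unknown | 20 Sep 2022 | Concomitant under 7.7 |
| Radiotherapy, 2022, month unknown | 20 Sep 2022 | Concomitant under 7.7 |
| Chemotherapy, start and stop both 2022 only | 20 Sep to 31 Dec 2022 | Not prior under 7.6 |
| Chemotherapy stop, September 2022, day unknown | 30 Sep 2022 | Not prior under 7.6 |
| Chemotherapy start 2022 only, stop 30 Jun 2022 known | Start 20 Sep 2022 | Still prior, but start falls after stop |

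Radiotherapy has one date, so the rule reclassifies it directly. For drugs, the stop-date rule does the reclassifying; the start-date rule alone only produces impossible intervals. Partial dates in an earlier year, or with a known month before the dosing month, stay before first dose.

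**2. Share of partial records caught.** Assume first-dose dates spread evenly over a 365-day year and a true date (radiotherapy date or drug stop date) g days before first dose.

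- Month missing: the date falls in the dosing year with probability (365 − g)/365. At g = 28, 337/365 = 92%; at 90, 275/365 = 75%; at 180, 185/365 = 51%.
- Day missing: the date falls in the dosing month with probability Σ max(0, Lₘ − g)/365, where Lₘ is the length of month m. At g = 15, (365 − 180)/365 = 51%; at 21, (365 − 252)/365 = 31%; at 28, (365 − 336)/365 = 8%; at 60, 0%.

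These are shares of records that are already partial. The documents do not say how common partial dates are.

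**3. Subsequent therapy.** Assume first dose 15 March 2022, post-baseline scans on 26 April, 7 June and 19 July, last dose 28 June, and no progression. PFS is censored at the last scan on or before the new therapy. The TEAE window ends at the earlier of last dose + 30 days (28 July, day 136) and the day before the new therapy.

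| Collected | Date chosen | PFS censored | TEAE window ends |
|---|---|---|---|
| July 2022 | earliest, 1 July | day 85 | day 108 |
| July 2022 | latest, 31 July | day 127 | day 136 |
| 2022 only | earliest after last dose, 29 June | day 85 | day 106 |
| 2022 only | latest, 31 December | day 127 | day 136 |

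The unwritten choice moves this patient's PFS censoring by 127 − 85 = 42 days. It moves the TEAE window by 136 − 108 = 28 days (month known) or 136 − 106 = 30 days (year only).

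**The case against.** **The prior-therapy point may never reach a table.** SAP 5.1.4 summarises prior systemic therapy and prior radiotherapy separately, and the listings in 7.6 and 7.7 draw on the concomitant medication and procedure forms. The documents do not show that prior-treatment forms feed the concomitant summaries. This limits the likely size. It does not rescue the rule: 4.3.2 and 4.3.3 name these records as inputs to the prior/concomitant decision, and for the cases above they give the wrong answer. SAP 4.3 also does not name prior radiotherapy among the dates that may be partial, although 4.3.3 provides for it.

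**Wider harm is not supported.** A reader might infer that every partial prior-therapy record in the dosing year is misclassified. That is not so: a drug with a known stop date before first dose stays prior. A reader might also infer false protocol deviations or distorted response data. Deviations come from a log (5.2.2), response comes from the response forms (6.1), and listings show dates as collected (4.3).

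**The worst case for new therapy is hypothetical.** Borrowing 4.3.2 for a year-only date would put new therapy on Day 1, leave no post-baseline scan for PFS and close the TEAE window before dosing. The SAP does not prescribe this: 4.3.2 is confined to prior/concomitant classification, and 4.3.4 bars unstated imputation.

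**Other safeguards help.** Missing dates are queried, and the TEAE window is capped at 30 days after last dose. Off-treatment scans stop when another therapy starts (protocol 9.9), so the last scan will often be the right censoring scan. These reduce the number of affected patients but do not supply the rule.

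**A single earliest-date rule would not be neutral.** This stands. In the year-only example it ends the TEAE window on the day of last dose and could drop real post-dose events.

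**Conclusion.** The concern holds in a limited form. As written, 4.3.2 and 4.3.3 reclassify known prior treatment when a radiotherapy date or a systemic-therapy stop date lacks its day in the dosing month or its month in the dosing year. They can also place an imputed start after a known stop. The consequence is wrong prior/concomitant classification in descriptive summaries. Collected dates in listings, the deviation log and the response data are untouched.

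The secondary point is a gap in the rules, not a stated error. It matters for PFS and DoR only in patients who start new therapy without documented progression, and for TEAEs only within 30 days of last dose. The expansion-phase primary endpoint, ORR, does not depend on this date.

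The number of records affected by either point is unknown. The shares and day counts above rest on the assumed dates and on evenly spread first-dose dates.

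**What to change.** 1. **Prior treatment (4.3.2 and 4.3.3).** State that records from the prior systemic therapy, prior radiotherapy and prior surgery forms are classified as prior. Cap their imputed start and stop dates at the day before first dose, with start no later than stop. The present rules can stay for other medications and procedures.

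2. **Subsequent therapy (new subsection of 4.3).** Extend the principle already used for death dates in 4.3.4.
   - For PFS and DoR: the earliest date that fits the recorded month or year and other data, and falls after the last study dose.
   - For the TEAE window: the latest consistent date, still capped at 30 days after last dose.

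The cost is a few sentences in the SAP and a small programming change. The first change has no real downside. The second uses two imputed dates for one event, which the SAP should state openly: the PFS date may give up some follow-up (42 days in the example), while the safety date avoids discarding real events.

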# **4.3.3.** Missing Procedure Date

For records with a missing procedure (including prior radiotherapy) date, the following procedure will be employed for use in determining whether the procedure is prior or concomitant:

- Procedure dates with a missing day and non-missing month will be assumed to occur on the first day of the non-missing month, except for procedures occurring in the first month of dosing, in which case the date will be the first day of dosing.
- Procedure dates with missing month will be assumed to occur on the first day of the non-missing year (ie, January 1), except for procedures occurring in the first year of dosing, in which case the date will be the first day of dosing.

#### 4.3.4. Missing Death Date

For records with a partial death date, the following procedure will be employed for use in deriving time-to-event variables (eg, PFS).

• The death date will be imputed by the earliest possible date that is not contradicting with any other available data in the database.

All other data will be reported as they are collected. No imputation methods will be used to replace missing data unless otherwise stated in this document.

# 4.4. Multiple Assessments for the Same Assessment Time Point

In general, no by-visit analyses is planned for this study, unless otherwise indicated for a specific parameter.

# 4.5. Multiple Study Centers

Patients from all study centers will be pooled for analyses. No adjustment for study center will be made.

# 4.6. Covariate Adjustment in Primary Analysis

As the sample size is relatively small, no covariate adjustment will be made.

# 4.7. Sample Size Reassessment

Not applicable.

## 4.8. Interim Analyses

Not applicable.

#### 4.9. Test Sizes

No statistical hypothesis test will be performed.

## 4.10. Hypothesis Testing and Multiple Comparisons

No statistical hypothesis test will be performed, and there will be no multiple comparisons.

# 4.11. Analysis Populations

#### 4.11.1. Safety Population

Safety population consists of all participants who received at least one dose of study drug. This population will be used for analyses of safety, PK, pharmacodynamics, and immunogenicity. It will also be used for summary of baseline data and analyses of progression-free survival (PFS).

#### 4.11.2. Response Evaluable Population

Response evaluable population consists of all participants who received at least one dose of study drug, had baseline measurable or non-measurable disease, and had at least one post-baseline radiographic tumor assessment or discontinued study drug due to clinical progression or death if no post-baseline tumor assessment. This population will be used for summary of tumor assessment data and analyses of response rates.

# 4.12. Data Display Characteristics

Data displays produced for this study will include summary tables, data listings, and figures. Data listings will be produced for all recorded data as described in Section 5, Section 6, and Section 7. Summary tables will be produced as specified in Section 5, Section 6, and Section 7. Additional data listings will be produced for outcome measures that involve extensive procedures to derive the analyzed outcomes. Figures will be produced when specified in Section 5, Section 6, and Section 7.

Data listings will report the data recorded on the eCRF or derived for each patient. Data will be ordered by patient number, and date/time of assessment. When expedient, additional levels of ordering hierarchy may reflect subsets of assessments within patient. Data listings will not display patient initials.

The summary statistics displayed will be a function of the type of data associated with the summarized assessment. Unless stated otherwise in relevant sections, Section 5, Section 6, and Section 7, continuous data will be summarized with the number of non-missing values, mean, standard deviation, minimum, median, and maximum. Categorical data will be summarized with

the number of non-missing values and the numbers of values equal to each of the possible values. Percentages of patients with each of the possible values will be calculated from the number of patients in the corresponding analysis population, unless stated otherwise. Some continuous variables may also be grouped into categorical levels and evaluated in frequency tables.

#### 5. PATIENT ACCOUNTABILITY

Patient accountability will be summarized for the Safety population.

#### **5.1.** Patient Characteristics

Patient characteristics will be summarized and listed.

#### 5.1.1. Demography

The following patient characteristics collected at the screening visit will be summarized:

- Age
- Sex
- Ethnicity
- Race

All demography data, including informed consent date, will be listed.

#### 5.1.2. Height, Baseline Weight, and BMI

Height and baseline weight as well as BMI will be summarized and presented.

#### **5.1.3.** Medical History

Medical history will be coded using Medical Dictionary for Regulatory Affairs (MedDRA), associating lower-level terms with preferred terms (PTs) and system organ classes (SOCs) by the primary hierarchy. Medical histories will be summarized as the number and percentage of patients who reported at least 1 medical history event; and number and percentage of patients who reported at least 1 medical history event in each SOC. Within each SOC, tables will display the number and percentage of patients reporting at least 1 medical history event as designated by PT. All medical history information will also be listed.

#### **5.1.4.** Disease Characteristics and Prior Therapy

Listings of all collected data related to disease characteristics and prior therapy will be provided. A summary of the following elements will also be provided:

- Baseline ECOG performance status
- Baseline left ventricular ejection fraction (LVEF) results
- Primary tumor type

- a) Non-Squamous non-small cell lung cancer (NSCLC)
- b) Triple Negative Breast Cancer (TNBC)
- c) Colorectal Cancer (CRC)
- d) Gastroesophageal Cancer
- e) Pancreatic Cancer
- Disease status (Locally Advanced Disease, Metastatic Disease, both)
- Disease stage at diagnosis (I, II, III, IV, Unknown)
- Time since initial diagnosis (months)
- Prior cancer surgery (yes/no)
- Prior radiotherapy (yes/no)
- Prior systemic therapy

# 5.2. Patient Disposition

#### 5.2.1. Disposition

A summary of patient disposition will present the number of patients enrolled and the reason for treatment and study discontinuation.

The number and percentage of patients who withdrew for each reason on the End-of-Treatment and End-of-Study eCRF forms will be provided.

#### **5.2.2.** Protocol Deviations and Population Inclusions

Protocol deviations will be captured in a protocol deviation log. A listing of major and minor protocol deviations will be provided.

#### 6. EFFICACY ANALYSES

The efficacy analyses will be performed on the Response Evaluable Population.

## **6.1.** Efficacy Outcomes

The response outcomes such as best overall response and overall response rates will be determined based on the response data recorded on the Response and Response Follow-up eCRFs between the date of the first dose of study drug and the date of study discontinuation.

#### 6.1.1. Progression-free survival (PFS)

Progression-free survival will be defined as the time from the first dose date of study drug to the date of first documented progression or death from any cause, whichever occurs first. The documented progression is determined by objective assessment of disease per RECIST v1.1. For participants who are not known to be dead or progressed at the time of data cut-off for PFS

analysis, the PFS will be censored at the date of the last tumor assessment. Specifically, the following censoring rules (Table 2) will be applied to the PFS analysis.

**Table 2:** Censoring rules for PFS

Situation	Date	Outcome	
No baseline tumor assessments	First dose date	Censored	
Death prior to first scheduled tumor assessment	Date of death	Event	
No post-baseline tumor assessments in absence of death prior to first scheduled tumor assessment	First dose date	Censored	
Documented progression	Date of progression	Event	
Initiation of alternative anti-cancer treatments in absence of documented progression	Date of last tumor assessment on or prior to initiation of such treatment	Censored	
Death or documented progression immediately after missing 2 or more consecutive scheduled tumor assessments (i.e, documented progression or death date - last radiological assessment date +1 ≥ 105 days)	Date of last tumor assessment prior to missed assessments	Censored	

